**Effectiveness of proprioceptive neuromuscular facilitation for improving for
shoulder biomechanical parameters, function, and pain after axillary lymph node
dissection: a randomized controlled study**

Study Protocol and Statistical Analysis

NCT NO: 10840098-604.01.01-E.184

Ethics committee approval date: 25/12/2019

Document update date: 19/01/2022

Breast cancer is the most common type of cancer affecting women of all ages worldwide. An increase in the incidence of breast cancer is observed with the effect of widespread screening programs today. Improved and comprehensive treatment options (surgery, radiotherapy, systemic adjuvant and neoadjuvant therapy, hormonal therapy) have increased the survival rate and life expectancy. This has necessitated a focus on the short, medium and long term complications of breast cancer treatment and their management. Axillary lymph node dissection and radiotherapy are associated with pain, physical symptoms, and decreased functional abilities in the upper extremity. This study aimed to compare the potential effects of proprioceptive neuromuscular facilitation (PNF) technique on muscle strength, pain and functionality in this patient group with progressive resistance exercise (PRT).

Inclusion Criteria:

- Individuals diagnosed with stage II-III breast cancer
- 30-65 years old
- ALND was performed by the same surgeon regardless of breast resection level.
- Receiving radiotherapy
- Individuals who spent the first six months after surgery were included in the study.

Exclusion Criteria:

- Diagnosed with stage IV or metastatic breast cancer
- Developing bilateral breast cancer
- Developing lymphedema in the postoperative period
- Any contraindication to exercise
- Participating in any physiotherapy program for the upper extremity in the last 6 months
- Have significant cardiac, pulmonary or metabolic comorbid disease
- Individuals with communication problems were excluded from the study.

The study was designed as a randomized, controlled, single-blind, prospective study to compare the effectiveness of PNF technique and progressive resistance exercise. Patients who applied to Istanbul Medipol University General Surgery Department for routine control after breast cancer treatment were determined. Individuals who were willing to participate and met the inclusion criteria were divided into 3 groups (PNF, progressive resistant ex., control) using the website www.randomizer.org.

Proprioceptive Neuromuscular Rehabilitation group

The PNF technique was performed in the supine position with the hip joints of the patients in 30° flexion and the lower extremities in semi-flexion. The application was performed in 2 different diagonal and 4 different patterns (flexion-abduction-external rotation/extension-abduction-internal rotation, and flexion-adduction-external rotation/extension-abduction-internal rotation) of the upper extremity. When starting the exercise, the muscles were first brought to their longest position and the patient was asked to move in the direction of the pattern with resistance (concentric contraction) and to maintain this position for 6 seconds at the end of the pattern (isometric contraction). Then, while the therapist was taking the patient's arm to the starting position, the patient was asked to prevent movement (eccentric contraction). All of these moves counted as one repetition. 3 sets of 8-12 repetitions were performed for each pattern.

Progressive Resistance Exercise Group

Strengthening exercises targeting the upper extremity main muscles were applied to the PRE group with progressive resistance. Dumbbells and sandbags were used as resistance equipment. resistance intensity; 50-80% of a repetition maximum (RM) was determined according to the patient's tolerance. The exercises were applied as 8-12 repetitions and 3 sets. A rest period of 60-90 seconds was allowed between each set. After the 4th week of the training, 1 RM was measured again and the resistance density was updated. The 8 strengthening exercises to be applied were created by taking examples from the literature and in accordance with the "Guidelines for implementing exercise programs exercise programs for cancer patients". These exercises are: "dumbbell fly", "triceps extension", "biceps curl up", "one-arm bent over row", "dumbbell sides rise", "lifting the arm forward", "wrist curl" and side lying shoulder internal - external rotation".

Control Group

The patients in the control group were instructed to continue their usual daily lives (not changing their physical activity levels, diet, drug use, etc.) until the date of re-evaluation after the initial evaluation. Information was given about the upper extremity normal range of motion exercises that they could apply at home, and a brochure was given.

Primary Outcome Measure:

1. Isokinetic dynamometer

Humac Norm, model 770, Computer Sports Medicine Inc., Stoughton, USA was used to biomechanically evaluate shoulder flexors/extensors, abductor/adductors, internal/external rotators. Muscle strength was measured at 60°/s, muscle strength at 120°/s, endurance at 180°/s angular velocity and in concentric/concentric mode. 5 repetitions at 60°/s and 120°/s angular velocity, and 15 repetitions at 180°/s angular velocity were performed at the measured active range of motion. The measurement was performed only on the operated side upper extremity. A rest period of 2 minutes was provided between series of each muscle group and 5 rest periods between different movement patterns. For each angular velocity, the first trial was subtracted, and the average peak torque value of the remaining repetitions (the force produced by the individuals at the maximum during the angular velocity) was recorded in Newton-meters (Nm). It was applied before and after the 8-week treatment protocol.

2. Disabilities of the Arm, Shoulder, and Hand (DASH)

The scale includes 30 questions about symptoms (5 items) and functionality (25 items). In this study, business/sport-specific additional modules of the scale were not used. Each item offers 5 answer options and is scored on a likert scale from 1 to 5. 1: reflects 'no difficulty' and 5: reflects 'serious difficulties'. The resulting scores for all items are then used to calculate the total score from 0 (no disability) to 100 (most severe disability) (16). It is accepted as the most consistent test in terms of construct validity and responsiveness in examining upper extremity problems in individuals undergoing breast cancer treatment. It was applied before and after the 8-week treatment protocol.

3. Visual Analogue Scale (VAS)

The patients were asked to mark their pain levels in the breast, shoulder and axilla regions on the affected side during rest and activities of daily living on a 10 cm scale (0=no pain, 10=worst pain ever experienced). The distance (cm) between the zero point and the point marked by the patient indicates the level of pain. It was applied before and after the 8-week treatment protocol.

4.Global Rating Of Change Scale (GRC)

The Global Rating of Change Scale (GRC) contains a single question in which the patient can rate how much he has improved retrospectively from his own perspective. The validity and reliability of the GRC scale has been verified and is widely used in the assessment of change for musculoskeletal problems. 7 different answers (-3: much worse, 2: worse, -1: slightly worse, 0: the same, 1: a little better, 2: quite good, 3 They were asked to answer by choosing one of the :much better) options. In scoring, scoring can be done according to a 7-point Likert evaluation, as well as calculations can be made using negative scores. This scale was applied only to the study groups in the post-treatment measurement. It was applied only at the end of the 8-week treatment protocol.

Statistical analysis

In the descriptive statistics of the data, mean, standard deviation, median minimum, maximum, frequency and ratio values were used. The distribution of variables was measured with the Kolmogorov-Smirnov test. Kruskal-wallis, mann-whitney u test was used in the analysis of quantitative independent data. Wilcoxon test was used in the analysis of dependent quantitative data. Chi-square test was used in the analysis of qualitative independent data, and fischer test was used when the chi-square test conditions were not met. SPSS 27.0 program was used in the analysis.

Document update date: 19/01/2022

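### Allocation is described only by naming a website, and the stated between-arm tests cannot adjust for baseline values or for the deliberately unrestricted resection level

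*Combined protocol and SAP*

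**What the plan says.** The study design paragraph, after the Exclusion Criteria, calls the trial a "randomized, controlled, single-blind, prospective study" without saying who is blinded. Its only statement on allocation is that patients who were willing and eligible were "divided into 3 groups (PNF, progressive resistant ex., control) using the website www.randomizer.org". It gives no ratio, sequence type, blocking or stratification, and does not say who made or held the list or whether the next assignment was hidden.

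The Inclusion Criteria fix the surgeon but leave the breast operation open: "ALND was performed by the same surgeon regardless of breast resection level". Resection level is not mentioned again.

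Under Primary Outcome Measure, torque, DASH and VAS are measured before and after the 8-week programme. Their timing relative to allocation is not stated. The Global Rating of Change is taken only afterwards, and only in the study groups.

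Under Statistical analysis, the between-arm method for quantitative outcomes is "Kruskal-wallis, mann-whitney u test was used in the analysis of quantitative independent data", and within arms "Wilcoxon test was used in the analysis of dependent quantitative data". No adjusted or stratified analysis is listed.

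**The concern.** There are two separate issues.

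The first is entry. The three programmes look different to patient and therapist, dynamometry depends on effort, and DASH and VAS are self-reported. Later blinding can protect such a trial only in part, so a reader needs to know that whoever enrolled a patient could not foresee or redraw the assignment. The text puts willingness and eligibility before allocation, which helps only if the next assignment was hidden. That is not stated.

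The second is analysis. The trial admits a mixed surgical population and collects baseline values on its main outcomes, then compares arms with tests that have no place for either. If the arms differ by chance in surgical mix or starting level, the stated analysis cannot respond. It also forgoes the precision that the baseline values could give.

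**Working it through.** **Inputs.** The documents give no sample size, ratio, resection distribution, effect size or alpha, so there is no plan figure to reproduce. What follows is illustration under stated assumptions.

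**1. Chance imbalance in resection level.** Assume simple 1:1:1 allocation, with arm sizes multinomial(N; 1/3, 1/3, 1/3). Assume two resection types, one with prevalence p = 30% or 50%, with binomial counts in each arm. The quantity is the probability that the largest minus the smallest arm proportion is at least 0.20 (200,000 simulations).

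| Total N | p = 30% | p = 50% |
|---|---|---|
| 45 | 48% | 54% |
| 60 | 37% | 43% |
| 90 | 22% | 28% |

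Equal but unstratified arms do not remove this: at N = 60 the figures are 45% and 51%. They are higher partly because a gap of exactly 4 patients in 20 is attainable and counts as 20 points. Equal arm sizes alone therefore do not balance surgical mix.

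**2. What an imbalance does to one trial.** Shift in a two-arm contrast = difference in proportion × effect of resection type on the outcome. With a 20-point gap and an assumed effect of 0.5 SD, the shift is 0.20 × 0.5 = 0.10 SD. The documents give no effect of resection type, and the shift is proportional to it.

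**3. Type I error.** With an unadjusted binary factor worth 0.5 SD (prevalence 50%), simple allocation and no treatment effect, the Mann-Whitney test rejected in 4.9% of 4,000 trials at N = 45 and 4.4% at N = 60. The simulation standard error is √(0.05 × 0.95 / 4,000) = 0.34 points. There is no inflation above 5%: over repeated randomisations the test already allows for chance imbalance.

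**4. What baseline adjustment offers.** Let r be the correlation between baseline and 8-week values, with equal variances at both times. In large samples the variance of an arm contrast, relative to unadjusted 8-week means, is 1 − r² for ANCOVA and 2(1 − r) for change scores. The documents do not give r. Assuming 0.3 to 0.5:

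- ANCOVA: 1 − 0.09 = 0.91 to 1 − 0.25 = 0.75, which is 9% to 25% less variance than 8-week values alone.
- Change scores: 2 × 0.7 = 1.40 to 2 × 0.5 = 1.00, which is no better than 8-week values alone.

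These are results for means. They indicate the direction and rough size for rank ANCOVA but are not exact for it.

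**The case against.** The strongest reply is that most of this is silence, not a fault. A website can produce a balanced list, and someone outside recruitment may have held it. That stands. A reader might infer that there was no concealed, blocked or stratified list, or that patients were steered between arms. The documents support neither; they support only that these matters are not described.

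A reader might also infer that the arms will be unequal and the trial weakened. That needs simple allocation, which is not stated, and the loss would be small. For an assumed difference of 0.8 SD at two-sided 5%, pairwise power with equal arms against the average under simple allocation is 59.1% against 57.5% (N = 45), 71.6% against 70.2% (N = 60) and 87.3% against 86.5% (N = 90). The point does not rest on this.

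Nor does chance imbalance bias a properly randomised comparison on average, as step 3 shows. And no covariate model repairs selection at entry, so the adjustment below does not answer the concealment question.

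It is fair to add that no passage says resection level predicts torque, DASH or VAS. The background attributes arm problems to axillary dissection and radiotherapy, which all patients have. The case for resection level is that the plan deliberately lets it vary and adjusting for it is cheap. The case for the baseline values does not depend on it.

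Finally, the rank tests could be run on changes from baseline. The plan does not say so, and subtracting baseline is not the same as adjusting for it (step 4).

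**Conclusion.** The point holds in two limited parts.

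- **Allocation.** The description is too thin to exclude selection at entry. This is an unresolved risk, not a demonstrated defect, and no size can be put on it from the documents.
- **Analysis.** The stated between-arm tests cannot adjust for baseline values or resection level. Under simple allocation of an assumed 60 patients, some pair of arms differs by 20 points or more in resection mix in 37% to 43% of trials (22% to 54% over 45 to 90 patients). The harm is to precision and to the interpretation of the one trial that is run, not to type I error.

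The figures rest on assumed sample size, 1:1:1 simple allocation, two resection types at 30% to 50% prevalence and, for the 0.10 SD shift, an assumed 0.5 SD effect. The analysis change is worth making whatever those values are, because it uses data already collected or obtainable from surgical records.

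**What to change.** **In any case.** Make the between-arm comparison of 8-week torque, DASH and VAS a baseline-adjusted model with arm, baseline value of the same measure and resection level as terms: ANCOVA, or rank ANCOVA if rank methods are kept. The Global Rating of Change has no baseline and stays outside this. The cost is one or two degrees of freedom and taking resection level from surgical records. No extra patients or visits are needed.

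**If enrolment is still open.** Have the list generated and held by someone outside recruitment, and reveal each assignment only after consent and after the baseline measurements are recorded. State the ratio, the sequence type and who is blinded. If stratified blocks are used, choose block sizes that limit predictability. For example, with random blocks of 3 and 6, someone who knows the past assignments in a stratum but not the block sizes guesses the next arm correctly about 57% of the time, against 33% under simple allocation, and about 8% of assignments are certain.

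**If enrolment is finished**, as the past tense and the 19/01/2022 update may suggest. Report how the sequence was made, who held it and when baseline was measured relative to allocation. If the recruiter could see or redraw assignments, report allocation as unconcealed and limit the conclusions accordingly. The adjusted analysis is still available, with a note that it was specified after enrolment.

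### Does the repeated pattern name in the PNF description leave the experimental treatment undefined?

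*Combined protocol and SAP*

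**What the plan says.** The combined protocol and SAP describes the experimental treatment once, under the heading for the Proprioceptive Neuromuscular Rehabilitation group. The count and the bracketed list come in one sentence: "2 different diagonal and 4 different patterns (flexion-abduction-external rotation/extension-abduction-internal rotation, and flexion-adduction-external rotation/extension-abduction-internal rotation". The list holds two pairs. The first pair is "flexion-abduction-external rotation/extension-abduction-internal rotation" and the second is "flexion-adduction-external rotation/extension-abduction-internal rotation".

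Volume is tied to the pattern: "3 sets of 8-12 repetitions were performed for each pattern". The same paragraph gives the patient's position, the sequence of concentric, isometric and eccentric work within one repetition, and the 6-second hold.

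The first primary outcome, isokinetic dynamometry, is used "to biomechanically evaluate shoulder flexors/extensors, abductor/adductors, internal/external rotators". The Statistical analysis section compares groups with rank tests, and with chi-square or Fisher tests for categorical data. It does not refer to patterns, sets or repetitions.

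**The concern.** The sentence promises four patterns that differ from one another, yet the second member of each pair is the same. Read literally, the count and the list cannot both be right. The paragraph is the only definition of the treatment under test, so a reader has nowhere else to look. It is continuous prose with no sign of redaction or a broken table.

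Three things would be at stake if the list were literally what was done.

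- **Volume.** Sets and repetitions are given per pattern, so the amount of exercise depends on how many patterns there were.
- **Balance between the active arms.** The comparator is a list of 8 resistance exercises with the same range of sets and repetitions, so a smaller PNF count would widen the gap in volume.
- **Link to the outcome.** Abductor and adductor torque both belong to the first primary outcome. As printed, abduction appears in three of the four entries and adduction in one. Someone repeating the study could not tell from the text which movement directions were trained and how often.

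**Working it through.** **Inputs.** The announced count (2 diagonals, 4 patterns), the bracketed list, and the volume rule (3 sets of 8 to 12 repetitions for each pattern) all come from the PNF section. The comparator's 8 exercises, at 3 sets of 8 to 12, come from the Progressive Resistance Exercise Group section.

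**Step 1: reproduce the count.** Split the list at the comma for diagonals and at the slash for patterns.

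| Item | Announced | In the list |
|---|---|---|
| Diagonals (pairs) | 2 | 2 |
| Places for patterns | 4 | 2 × 2 = 4 |
| Distinct pattern names | 4 | 4 − 1 repeat = 3 |

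The number of pairs and the number of places both agree with the announcement. Only the number of distinct names does not.

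**Step 2: volume for one pass through the list.** Repetitions = patterns × 3 sets × repetitions per set.

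- Four places performed: 4 × 3 × 8 = 96, up to 4 × 3 × 12 = 144.
- Three patterns performed, none repeated: 3 × 3 × 8 = 72, up to 3 × 3 × 12 = 108.
- Difference: 1 − 72/96 = 25%.
- Four places performed exactly as printed, one pattern twice: the total is again 96 to 144, with 2 × 3 × 8 = 48 to 2 × 3 × 12 = 72 repetitions on the repeated pattern.

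The total therefore changes only if a place was left out. A wrong label in a place that was performed leaves it unchanged. Calling these totals per-session figures is an assumption, because the PNF section does not state how many sessions were given or say that the volume is per session. The 25% ratio does not depend on that.

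**Step 3: volume relative to the comparator.** If the comparator's sets apply to each exercise (also an assumption), it performs 8 × 3 × 8 = 192 to 8 × 3 × 12 = 288 repetitions. PNF is then 96/192 = 50% of that with four patterns and 72/192 = 37.5% with three. The active arms differ in repetition count under either reading, so equal volume was not a property of the design that the repeated label could have broken.

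**Step 4: does any analysis use the count?** The outcomes are torque, DASH, VAS pain and the global rating of change. The tests in the Statistical analysis section take group membership and outcome values as inputs. None takes the number of patterns. The document gives no sample size or power figure into which the count could enter.

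**The case for a change.** The strongest case for acting is that this sentence defines the treatment being tested, that it contradicts itself, and that correcting it costs little. The document does not show which entry is wrong, so a probable slip is still an unresolved one. The uncertain element is a movement direction, and abductor and adductor torque are among the measured outcomes. An experimental arm that cannot be reproduced exactly from its only description is a reporting weakness.

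That much stands for replication. The stronger consequences do not.

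- It does not follow that therapists delivered something other than four patterns. The paragraph is in the past tense and reports what was done, and nothing indicates that therapists worked from this sentence.
- It goes too far to say that results for those muscle groups could not be tied to a known treatment. Position, contraction sequence, hold, sets, repetitions and the two-diagonal structure are all stated. The open point is one label.
- The 25% shortfall requires a dropped place, for which there is no evidence.
- The first pair has abduction at both ends, but that is an error only if the members of a diagonal must be opposites. The document sets no such rule, so the remark adds nothing that can be settled here.

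The document also contains comparable slips: a missing minus sign in the global rating options, a rest period of 5 with no unit, and a repeated phrase in a guideline title. They make a one-label error a more natural explanation than a three-pattern treatment.

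**Conclusion.** The inconsistency is real and narrow: four places, three distinct names, one repeated entry. The most plausible explanation is a clerical slip in a single label, because the pairs and places match the announced count exactly. On that reading the volume is 96 to 144 repetitions for one pass through the list, whichever label is wrong. The 72 to 108 range, 25% lower, is conditional on an omission that nothing in the document indicates.

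No change to the plan follows. Correcting a label in an account of treatment already given alters neither what patients received nor how they were allocated, and it leaves every outcome and every test in the Statistical analysis section as it is. The count and the named patterns must be reconciled against the treatment records when the intervention is reported, which is an editorial task for the sponsor. This review takes no view on which entry is correct.

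The conclusion rests on two assumptions: that the past-tense wording reports actual delivery, and that four places in the list mean four were performed. If treatment records showed that fewer were performed, the description of the PNF arm and its volume would need to say so, but the planned group comparisons would still be computed in the same way.

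### Torque, DASH and VAS have baselines, but arms are compared only by rank tests without baseline adjustment, and no between-arm difference or confidence interval is planned

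*Combined protocol and SAP*

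**What the plan says.** The design paragraph of the combined protocol and SAP describes a "randomized, controlled, single-blind, prospective study to compare the effectiveness of PNF technique and progressive resistance exercise", with a control group as third arm.

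Under Primary Outcome Measure, the same sentence closes the entries for isokinetic torque, DASH and VAS: "It was applied before and after the 8-week treatment protocol". Each of these variables therefore has a baseline. The Global Rating of Change scale does not: "This scale was applied only to the study groups in the post-treatment measurement".

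The analysis plan is the single paragraph headed Statistical analysis. For comparing arms on quantitative outcomes it says "Kruskal-wallis, mann-whitney u test was used in the analysis of quantitative independent data". For paired data it says "Wilcoxon test was used in the analysis of dependent quantitative data". The summaries are purely descriptive: "In the descriptive statistics of the data, mean, standard deviation, median minimum, maximum, frequency and ratio values were used". A distribution check is listed ("The distribution of variables was measured with the Kolmogorov-Smirnov test"), but no alternative analysis depends on its result.

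**The concern.** The main question is a contrast between arms. For that contrast the plan offers p-values from rank tests and nothing else. Two things are missing.

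- **Baseline adjustment.** A baseline has been collected for every torque, DASH and VAS variable, but no comparison of arms is adjusted for it. Adjustment usually gains power, by an amount that depends on the correlation r between baseline and week 8 and on the shape of the data.
- **An effect estimate.** No between-arm difference and no interval is listed. If PNF and progressive resistance do not differ significantly, a reader cannot tell how large a difference the data still allow.

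The text also leaves open whether the rank tests use the week-8 value or the pre-post change. Taken alone, this is a missing detail. It matters here because the two tests can differ greatly in power, and neither is a baseline-adjusted comparison.

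**Working it through.** The plan states no sample size, alpha, power, effect size, SD or correlation, so there is no figure of its own to reproduce. All inputs below are assumptions.

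**Step 1: variance, normal data with equal SDs.** Taking the week-8 variance as 1, the variance of a change is 2(1 - r) and that of a baseline-adjusted value is 1 - r². The ratio of adjusted to change is (1 - r²) / [2(1 - r)] = (1 + r)/2.

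| r | change, 2(1 - r) | adjusted, 1 - r² | adjusted / change, (1 + r)/2 |
|---|---|---|---|
| 0.3 | 1.4 | 0.91 | 0.65 |
| 0.5 | 1.0 | 0.75 | 0.75 |
| 0.7 | 0.6 | 0.51 | 0.85 |
| 0.9 | 0.2 | 0.19 | 0.95 |

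A change beats the week-8 value only when r exceeds 0.5. In this setting, adjustment has a smaller variance than either.

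**Step 2: power on the rank scale.** Simulated with 20 per arm, a 0.6 SD latent shift at week 8 and two-sided 5%. In the floored case, values below zero are set to zero, so half the baseline values lie at the floor. The shift runs toward zero, because DASH and VAS both score 0 as the best state. Entries are approximate power in %; the last column is Quade minus the better of the other two.

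| Data | r | Mann-Whitney, week 8 | Mann-Whitney, change | Quade rank ANCOVA | Gain |
|---|---|---|---|---|---|
| Normal | 0.3 | 42 | 33 | 45 | 45 - 42 = +3 |
| Normal | 0.5 | 44 | 44 | 54 | 54 - 44 = +10 |
| Normal | 0.7 | 44 | 63 | 67 | 67 - 63 = +4 |
| Normal | 0.9 | 44 | 98 | 96 | 96 - 98 = -2 |
| Floored | 0.3 | 32 | 17 | 33 | 33 - 32 = +1 |
| Floored | 0.5 | 33 | 22 | 39 | 39 - 33 = +6 |
| Floored | 0.7 | 34 | 29 | 46 | 46 - 34 = +12 |
| Floored | 0.9 | 34 | 56 | 71 | 71 - 56 = +15 |

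Which listed test is better depends on r and on the data shape. At r = 0.9 on normal data they are 98 - 44 = 54 points apart.

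**Step 3: error rate with no true difference** (15 to 30 per arm; normal, lognormal and floored data). With the variable fixed, Mann-Whitney rejects in 4.2-5.4% of trials, Kruskal-Wallis in 4.3-5.3% and pairwise Quade in 4.5-5.5%. All keep the 5% level.

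**Step 4: which interval.** The Hodges-Lehmann shift on changes is the natural partner of a Mann-Whitney test, but it does poorly at a floor. With floored data improving toward zero and 20 per arm, it disagreed with the Quade test in 30-59% of trials. Its estimate was only about -0.1 SD for a 0.6 SD latent shift, because ties at zero dominate. An ANCOVA mean difference with heteroscedasticity-robust (HC3) errors had simulated 95% coverage of 95-97% on normal data, 93-96% on floored data and 88-94% on strongly lognormal data.

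**Step 5: the Wilcoxon test does not fill the gap.** It works within an arm. With 20 per arm and the same true standardised change in two arms (0.3, 0.5 or 0.65 SD), exactly one arm was significant in about 34%, 49% and 36% of runs.

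**The case against.** The strongest reply is that Kruskal-Wallis and Mann-Whitney tests are valid under randomisation, that a change score already uses the baseline, and that Quade's method is one of several acceptable choices. Much of this stands. The tests are valid, and the text does not exclude change scores. At r = 0.9 on normal data the change-score test does slightly better than Quade. The size of any gain rests wholly on assumed inputs. None of this supplies a between-arm difference or an interval.

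A reader might infer that the unnamed variable inflates the false-positive rate to 8-10%. The documents do not support that. The figure arises only if both the week-8 value and the change are tested and the smaller p-value is reported: 7.9-9.6% for Mann-Whitney and 8.0-9.7% for Kruskal-Wallis under the assumptions of step 3. The plan does not say that this is done.

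A second objection is that a rank test paired with a mean-difference interval can give conflicting answers. That is true and is a real cost. Using raw-scale ANCOVA for both would remove it, but on lognormal data shifted away from zero (20 per arm) its power was 39/44/54/86% at r = 0.3/0.5/0.7/0.9, against 47/54/68/97% for Quade.

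**Conclusion.** The point holds as an omission that should be fixed. For torque, DASH and VAS the plan has baselines but no baseline-adjusted comparison of arms, no between-arm difference and no confidence interval, in a trial whose purpose is to compare PNF with progressive resistance exercise. The listed rank tests are not invalid, and no inflated error rate follows from the text.

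Under the assumptions of step 2, the power gain over the better listed test runs from -2 to +10 points on normal data and from +1 to +15 on floored data improving toward zero. Against whichever test the plan does not make clear it is using, the loss could be much larger. Confidence is high for the omission and moderate for the size of the gain, since sample size, effect, r and data shape are all absent from the documents.

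**What to change.** For each torque, DASH and VAS variable:

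1. Make the between-arm test a baseline-adjusted comparison of the week-8 value on the rank scale: Quade rank ANCOVA with that variable's baseline as covariate, overall and then by pair, reporting PNF versus progressive resistance first.
2. Report each pairwise baseline-adjusted mean difference with a 95% confidence interval by one pre-named method, for example ANCOVA with HC3 errors. Do not mandate the Hodges-Lehmann shift on changes for VAS and DASH, which are prone to a floor.
3. State that the Quade p-value is the test and the interval is the estimate, because the two can disagree.
4. If Kruskal-Wallis and Mann-Whitney are kept as secondary tests, name one variable for them.
5. Leave out the Global Rating of Change scale, which has no baseline.
6. The paragraph is written in the past tense and the document is dated 19/01/2022. If results have been seen, label the adjusted analysis post hoc.

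The cost is a little analysis work and one degree of freedom per model, with no new measurements. Power may fall by up to about 4 points against the change-score test at r = 0.9 (15 per arm, normal data or floored data moving away from the floor). The HC3 interval should be read with care if an outcome is strongly skewed, given its 88-94% coverage on strongly lognormal data.
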